6.2 Observation Period

The Observation Period will begin with the first trabectedin + PLD dose administered after the signing of the ICF and will continue for up to a total of 12 months after that or until trabectedin treatment discontinuation, patient discontinuation for any reason or patient's death. PLD discontinuation is not a reason for Observation Period discontinuation. There are no predefined limits to the number of cycles administered. Trabectedin + PLD treatment can continue at the treating clinician's discretion.

Methods and timing of the imaging procedures will be determined by the treating clinician.

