6.2.2 Subsequent Visits during Observation Period

Subsequent visits will occur at the treating clinician's typical schedule. On each subsequent visit during the Observation Period, the following data, if available, will be collected:

- 1. Complete physical examination (including weight, height, and BSA).
- 2. Evaluation of performance status using ECOG/WHO PS score.
- 3. Safety assessment (all AEs including ADRs and SADRs).
- 4. Imaging procedures and results of imaging response evaluations will be collected, if they are available, during each cycle of the Observation Period of the study. Symptomatic response will also be collected.
- 5. Laboratory tests will be collected when available and based on the treating clinician's usual practice procedures. When available, those laboratory tests associated with ADRs and SADRs will be collected.
- 6. Data on trabectedin + PLD treatment administration.

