6.3 Follow-up Period

A follow-up visit will take place 1 month after the end of the Observation Period. For patients who discontinued trabectedin before 12 months after the Index date, an additional follow-up visit will be performed 12 months after the Index date, except for patients who are dead or have withdrawn consent. Follow-up information may be collected through phone calls with the patient or site visits by the patient.

For each follow-up visit, the following data will be collected, if available:

- Safety assessment (all AEs including ADRs and SADRs). Laboratory tests associated with ADRs and SADRs will be collected when available.
- Reason for discontinuation of treatment with chemotherapy, if applicable. Reason will include the following: treatment completed, PD, toxicity including grade, patient refusal, patient lost to follow-up, withdrawal of consent, inter-current illness of sufficient severity (specify), withdrawal for pregnancy, death (specify the cause), or other (specify).

- Best symptomatic response and best response (except for patients with confirmed PD at discontinuation or who had started a new treatment) and evaluation of treatment duration.
- Survival status.
- Subsequent non-trabectedin anti-cancer treatments that the patient received during the follow-up period, including regimen number, type of therapy, start and stop date, and best response observed for each regimen.

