5.3 Effectiveness

Overall Best Response

Overall best response for a patient is the best-observed disease response based on all response assessments available for each patient up to reported PD and prior to any subsequent anticancer therapy. The assessments of SD must occur at least once on or after day 42 to be considered for best response.

Objective Response (OR)

Objective response is defined as a best tumor response assessment of either complete response or partial response. Patients who prematurely discontinue without a tumor assessment will be considered non-responders.

Disease Control (DC)

Disease control is defined as a best tumor response assessment of CR, PR, or SD. Patients without a post-baseline tumor disease assessment will be considered to not have disease control.

Thus, for all patients:

If overall best tumor response = CR, PR or SD then: DC=1

Otherwise: DC=0

Progression-free Survival (PFS)

Time (in months) from day 1 to the earliest date of disease progression as reported by the investigator or death, regardless of cause, (whichever is first). Patients with no reported disease progression and alive will be censored at last contact date/last date known alive.

PFS = (date of progressive disease or death - date of day 1) / 30.4375

All tumor assessment dates will be based on the actual imaging dates reported by the investigator.

Overall Survival

Overall survival time is calculated as the number of days from day 1 to death (date of death - date of first dose). Time to death will be summarized in months. Patients who have not died (no record of death) or are lost to follow up will be censored at the date of last contact/last date known alive.

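### PFS is censored at last contact, the OS date, with no last-evaluation sensitivity analysis, so time after an unreported progression counts as progression-free

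*SAP*

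**What the plan says.** SAP 5.3 measures PFS from Day 1 to investigator-reported progression or death from any cause. It then says: "Patients with no reported disease progression and alive will be censored at last contact date/last date known alive". For OS, those with no death recorded "or are lost to follow up will be censored at the date of last contact/last date known alive". Best response, in the same section, is "based on all response assessments available for each patient up to reported PD and prior to any subsequent anticancer therapy"; PFS has no corresponding rule for new therapy. On dates: "All tumor assessment dates will be based on the actual imaging dates reported by the investigator".

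Protocol 10.3 and 10.4.3 define PFS and the Kaplan-Meier method without a censoring date, and Protocol 10.4 assumes that censoring is non-informative. SAP 9.4.1 describes one PFS analysis, and SAP 11.1 and 11.2 list one PFS table and one PFS plot. SAP 8.4 allows unspecified alternative methods if assumptions fail, but names none for PFS.

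On data collection, Protocol 6.2 says: "Methods and timing of the imaging procedures will be determined by the treating clinician". Under Protocol 6.2.2, "results of imaging response evaluations will be collected, if they are available". For the visits after treatment, Protocol 6.3 says: "For each follow-up visit, the following data will be collected, if available", and "Follow-up information may be collected through phone calls with the patient or site visits by the patient". Section 6.3 also exempts patients who have begun a new treatment from best-response collection. Footnote 7 of Table 1 (Protocol 7) places the final imaging before any other chemotherapy.

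**The concern.** A contact date shows that the patient was alive. It does not by itself show that her disease was evaluated and had not progressed. For OS that date is the right one. For PFS it credits all time up to contact as progression-free, whether or not anyone looked.

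Most patients give no difficulty: a reported progression is counted at its date, and a death is an event. The weak spot is the patient who stops trabectedin, starts another treatment with no progression recorded, and is reached at 12 months after the index date, possibly by telephone. Planned disease data thin out at the new treatment, but her PFS time continues to the contact.

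PFS is the primary endpoint of a descriptive study, so its median and fixed-time estimates are the main product. With one analysis only, a reader cannot tell how much of the progression-free time rests on disease evaluation. If the gaps differ by prior antiangiogenic use, the planned description by group is affected too.

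**Working it through.** **No plan figure to reproduce.** Protocol 10.1 and SAP 3.2 justify at least 300 patients by judgement, with no precision, event count or dropout rate. The calculations below are illustrations.

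**Inputs from the documents.** Median PFS 9.7 months and median OS 27.0 months on trabectedin + PLD in platinum-sensitive patients of the earlier phase III study (Protocol 1.1.3.1). Last contact 12 months after the index date; with the index one 3-week cycle after Day 1, that is 12 + 21/30.4375 = 12.7 months from Day 1.

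**Assumed, not in the documents.** Exponential PFS, the share of progressions not reported, and when and how many patients leave assessment. True 12-month PFS is then 0.5^(12/9.7) = 42.4%.

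**A. Progressions missed while assessments continue.** Let a random share u never be reported, ignore deaths, and let everyone be contacted through month 12.
- As written: S_obs(t) = u + (1 − u)·S(t), so the median is 9.7 × log2[(1 − u)/(0.5 − u)].
- Censored at last evaluation: the hazard is about (1 − u) times the true one, so the median is 9.7/(1 − u).
- Example, u = 10%: as written 9.7 × log2(0.9/0.4) = 11.35; last evaluation 9.7/0.9 = 10.78.

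| u | Median, as written | Median, last evaluation | 12-month PFS, as written | 12-month PFS, last evaluation |
|---|---|---|---|---|
| 5% | 10.46 | 10.21 | 45.3% | 44.3% |
| 10% | 11.35 | 10.78 | 48.2% | 46.2% |
| 20% | 13.73 | 12.12 | 53.9% | 50.4% |

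The last as-written median lies beyond 12.7 months and would not be reached in practice. Last-evaluation censoring reduces this bias but does not remove it.

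**B. Patients leave assessment but stay in contact.** Simulation: death = progression time + exponential time with median 27.0 − 9.7 = 17.3 months. A fraction f of those progression-free at month 5 leaves assessment and stays in contact to 12.7 months. At f = 20% this is 0.20 × 0.5^(5/9.7) = 0.20 × 0.70 = 14% of all patients. Each later progression is reported with probability p; an unreported one becomes an event only at death. Medians in months for f = 20%, which agree within 0.1 month between repeat runs:

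| Later progressions reported (p) | 0% | 50% | 60% | 80% | 100% |
|---|---|---|---|---|---|
| As written | 10.9 | 10.3 | 10.1 | 9.9 | 9.7 |
| Last evaluation, no later non-progression evaluation recorded | 9.7 | 9.3 | 9.3 | 9.2 | 9.1 |
| Last evaluation, such evaluations recorded as fully as progressions | 9.7 | 9.7 | 9.7 | 9.7 | 9.7 |

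Twelve-month PFS as written is about 47% with none reported and 44.8% with half. For f = 10, 30 and 40% the as-written median is 10.3, 11.8 and not reached with none reported, and 10.0, 10.6 and 10.9 with half.

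If those who leave have twice the hazard and none of their progressions is reported, the truth is 9.0, as written gives 10.8 and last evaluation 9.6. The two rules need not bracket the truth.

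**C. Sampling error for scale.** With 300 patients and no censoring before the median, SE(S) = sqrt(0.25/300) = 0.0289. The density at the median is 0.5 × ln 2/9.7 = 0.0357. SE(median) = 0.0289/0.0357 = 0.81, and 9.7 ± 1.96 × 0.81 gives 8.1 to 11.3 months.

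**The case against.** The rule suits the endpoint. PFS rests on progression as the investigator reports it. Criteria other than RECIST are accepted, and symptomatic response is collected, so a clinic contact may itself be a disease evaluation. Protocol 4.4.1 encourages follow-up until death or end of study. Protocol 6.3 collects best response at follow-up for patients without confirmed progression at discontinuation or new treatment, and Table 1 marks response and imaging there. This stands: last-contact censoring can be defended as primary, and the main blind spot is narrower than all patients off treatment. Collection remains conditional on availability, so a gap is left.

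The alternative is also imperfect. In part B with no later non-progression evaluations recorded, the two rules err about equally near 60% reporting (+0.41 and −0.45 months at f = 20%); above that, the rule as written is closer to the truth. In part A the alternative remains biased upward. Both points stand, and they argue for showing both analyses.

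The part B shift at f = 10 to 20% lies inside the sampling interval. That is true, but the bias is systematic: a larger sample does not shrink it, and the reported interval does not contain it.

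A reader might infer that SAP 5.3 contradicts itself by stopping best response at new therapy but not PFS. It does not. Best response is cut at new therapy, whereas PFS counts progression or death regardless of later therapy; these are different targets.

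**Conclusion.** The point holds as a cheap improvement. The primary endpoint is censored at a survival date, no second PFS analysis is pre-specified, and time after an unreported progression counts as progression-free until death or last contact. The direction of that bias is upward. Its size depends on how many progressions go unreported, which the documents do not give. The illustrations run from no shift with full reporting to a median that is not reached in the most extreme case, and they rest on the exponential model and the assumed shares.

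A reader might go further and conclude that the censoring rule is wrong, that the study's PFS will be inflated, or that progression after trabectedin cannot be recorded. The documents support none of these. The follow-up list does not name a progression date as a separate item, but it collects best response, names progression among the reasons for stopping, and does not prevent an investigator from reporting progression.

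**What to change.** In SAP 5.3 and 9.4.1, before database lock (November 2019 in the protocol synopsis):

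- Keep last-contact censoring as primary if the sponsor prefers it. Pre-specify one PFS sensitivity analysis that censors patients without progression or death at the last dated disease evaluation showing no progression, or at Day 1 if there is none.
- State that a scan after Day 1 that serves as baseline under SAP 5.1 does not count as a non-progression evaluation. State also which date a non-imaging evaluation takes, since 5.3 refers only to imaging dates.
- Report the gap from last evaluation to last contact and the number censored at Day 1, overall and by prior antiangiogenic use.
- For new anticancer therapy begun before progression, report the number of patients and analyse PFS both ways: censored at the last evaluation before it, and with its start counted as an event. Censoring there is likely informative, so one version alone would not be enough.
- Leave OS unchanged.

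The cost is a few definitions, the derived evaluation date and the extra Kaplan-Meier runs, with no new patient procedure. SAP 8.2 expects tumour assessment dates to be complete, and Protocol 6.3 collects start dates of subsequent therapy.

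State the downsides beside the results: wider intervals; downward bias if later progressions are reported without matching non-progression evaluations (9.1 against 9.7 in part B); and residual upward bias if progressions are missed while assessments continue (part A). If 10% of patients had no dated non-progression evaluation (assumed), about 12 of 300 would be censored at Day 1 with all their progressions reported and about 26 with none, which is why that count should be shown.

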5.4 Safety

Adverse Events

All AEs (serious and non-serious, related and not related) reported from Day 1 of study treatment to 30 days post last dose of study treatment.

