8.2.2 Collection of Safety Information in the eCRF

The investigators are responsible for ensuring that all AEs (serious and non-serious, related and not-related) that occur after first dose of trabectedin until 30 days after last dose administered are reported using the applicable eCRF page within 15 calendar days from its knowledge. Beyond this period of time, only ADRs suspected to be related to trabectedin will be reported to the PharmaMar Pharmacovigilance Department.

All SADR with the study treatment must be followed after discontinuation until the event or its sequelae resolve or stabilize at an acceptable level to the treating physician.

Non-serious ADRs also will be collected in the pharmacovigilance database. The non-serious ADR will be retrieved by the Contract Research Organization (CRO) from the CRF and will be provided in a line listing on a monthly basis.

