9.5 Safety Analyses

9.5.1 Adverse Events

A solicited reporting system of AEs (serious and non-serious, related and not related) was used during this study, from the beginning of trabectedin + PLD treatment.

Whenever possible the investigator recorded the diagnosis, classified each adverse event in regards of seriousness and causal relationship to study drugs (trabectedin + PLD), and reported severity (grade).

AEs will be coded in the Medical Dictionary for Regulatory Activities (MedDRA) version 17.0 or higher by system organ class and a preferred term. Each event will be graded according to medical record documentation as 1 = mild, 2 = moderate, 3 = severe, 4 = disabling or life threatening consequences, and 5 = death.

The descriptive summaries presenting treatment emergent AEs will include AEs reported from Day 1 of study treatment to 30 days post last dose of study treatment. AE summaries will use the patient's maximum severity reported for each system organ class and preferred term. The corresponding summaries will be presented for AEs and SAEs grade 3 or higher.

Patient incidence of adverse drug reactions (ADR) related to trabectedin and related to PLD, respectively, will be tabulated by system organ class, preferred term and severity grade for all drug reactions and serious drug reactions. The corresponding summaries will be presented for ADRs and SADRs grade 3 or higher. ADR's relationship to treatment reported as unknown will be assumed to be related to both trabectedin and PLD.

In addition, and complementing the summaries above, AEs, SAEs, ADRs and SADRs will also be summarized by preferred term only, and in descending order of frequency.

A summary table will also be produced summarizing all event summaries and will include, AEs, SAEs, ADRs, SADRs, those leading to treatment discontinuation, and fatal events on study.

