11.1 Planned Tables

Category	Table Title
Disposition	Summary of Enrollment by Country and Site
Disposition	Reasons for Non-participation
Disposition	Summary of Inclusion and Exclusion Criteria
Disposition	Patient Disposition
Demographics and Baseline	Demographics and Baseline Characteristics
Demographics and Baseline	Medical History
Demographics and Baseline	Prior Anticancer Therapy
Demographics and Baseline	Baseline Imaging
Effectiveness - Primary Endpoint	Progression-free Survival
Effectiveness - Secondary Endpoint	Best Tumor Response
Effectiveness - Secondary Endpoint	Overall Survival
Effectiveness	Summary of Symptomatic Response
Other Secondary Endpoints	Summary of ECOG Performance Status
Treatments - Secondary Endpoints	Exposure to Trabectedin
Treatments - Secondary Endpoints	Trabectedin Dose Modification
Treatments - Secondary Endpoints	Exposure to PLD
Treatments - Secondary Endpoints	PLD Dose Modification
Treatments - Secondary Endpoints	Subsequent Anticancer Therapy after Stopping Trabectedin
Safety	Overall Summary of Patient Incidence of Treatment-Emergent Adverse Events
Safety	Overall Summary of Patient Incidence of

Category	Table Title
	Treatment-Emergent Adverse Drug Reactions
Safety	Treatment-Emergent Adverse Events
Safety	Treatment-Emergent Adverse Drug Reactions Related to Trabectedin
Safety	Treatment-Emergent Adverse Drug Reactions Related to PLD
Safety	Treatment-Emergent Serious Adverse Events
Safety	Treatment-Emergent Serious Adverse Drug Reactions Related to Trabectedin
Safety	Treatment-Emergent Serious Adverse Drug Reactions Related to PLD
Safety	Treatment-Emergent Adverse Events Grade 3 or Higher
Safety	Treatment-Emergent Grade 3 or Higher Adverse Drug Reactions Related to Trabectedin
Safety	Treatment-Emergent Grade 3 or Higher Adverse Drug Reactions Related to PLD
Safety	Treatment-Emergent Serious Adverse Events Grade 3 or Higher
Safety	Treatment-Emergent Grade 3 or Higher Serious Adverse Drug Reactions Related to Trabectedin
Safety	Treatment-Emergent Grade 3 or Higher Serious Adverse Drug Reactions Related to PLD
Safety	Treatment-Emergent Adverse Events in Descending Order of Frequency
Safety	Treatment-Emergent Adverse Drug Reactions Related to Trabectedin in Descending Order of

Category	Table Title
	Frequency
Safety	Treatment-Emergent Adverse Drug Reactions Related to PLD in Descending Order of Frequency
Safety	Treatment-Emergent Serious Adverse Events in Descending Order of Frequency

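### Related reactions starting more than 30 days after the last dose are collected at follow-up but enter no planned AE or ADR table, and the protocol gives two rules for recording them

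*SAP*

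**What the plan says.** Safety of the combination is a secondary objective in both documents (protocol 2.2, SAP 2).

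**Collection.** Protocol 6.3 asks for the following at each follow-up visit, where available: "Safety assessment (all AEs including ADRs and SADRs). Laboratory tests associated with ADRs and SADRs will be collected when available". Table 1 also marks the safety assessment in the follow-up column. One visit comes a month after the Observation Period ends. For patients who stop trabectedin within 12 months of the Index date, the same section adds: "an additional follow-up visit will be performed 12 months after the Index date, except for patients who are dead or have withdrawn consent".

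**Recording.** Protocol 8.2.2 has sites enter all AEs in the eCRF up to 30 days after the last dose. It then says: "Beyond this period of time, only ADRs suspected to be related to trabectedin will be reported to the PharmaMar Pharmacovigilance Department".

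**Analysis.** SAP 5.4 takes AEs of any seriousness and any relationship "reported from Day 1 of study treatment to 30 days post last dose of study treatment". SAP 9.5.1 repeats the limit: "The descriptive summaries presenting treatment emergent AEs will include AEs reported from Day 1 of study treatment to 30 days post last dose". Protocol 10.4.5 has the same AE window. The ADR sentence in SAP 9.5.1 starts "Patient incidence of adverse drug reactions (ADR) related to trabectedin and related to PLD, respectively, will be tabulated by system organ class" and gives no window of its own, nor does its counterpart in protocol 10.4.5. The ADR tables in SAP 11.1 carry titles such as "Treatment-Emergent Adverse Drug Reactions Related to Trabectedin".

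**The concern.** A 30-day limit is reasonable for all-causality AEs, because later events are increasingly due to the disease or to subsequent therapy. It is harder to justify for events that the investigator has attributed to trabectedin or PLD. If those are dropped because of their onset date, ADR and SADR incidence is understated for a stated secondary objective, and the safety information from the 12-month visit has no place in the AE or ADR tables.

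The recording rules add a second problem. Under 6.3 a site records all AEs at the 12-month visit. Under 8.2.2 its eCRF duty has ended, and only trabectedin-related reactions go on, to the sponsor's pharmacovigilance department. Two sites could follow the protocol and leave different data in the study database.

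**Working it through.** The documents give no figure to reproduce here. The check is a comparison of windows, a count of tables and an illustration of the time gap.

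**1. Does the 30-day limit reach ADRs?** SAP 5.4 applies the window to AEs whether related or not. Protocol 8.2 treats a related AE as an ADR. ADRs therefore fall inside the 5.4 definition, and nothing in SAP 9.5.1 overrides it. The table titles point the same way. This is a strong inference, but the limit is not stated for ADRs.

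**2. Count of planned ADR/SADR tables (SAP 11.1).** There is one overall summary. Then there are four families (ADR, SADR, grade 3 or higher ADR, grade 3 or higher SADR), each for two drugs and in two layouts (the standard table, and preferred terms by descending frequency):

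1 + 4 × 2 × 2 = 17.

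All 17 are titled treatment-emergent. No late-onset or post-treatment ADR table or listing appears.

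**3. What still shows after day 30?**
- SAP 9.2 summarises all deaths with cause at end of study, separately from deaths within 30 days of the last trabectedin dose.
- SAP 9.5.3 summarises clinically significant laboratory results with no stated cut-off, and event-related tests are collected in follow-up. A late laboratory value could therefore be tabulated while the reaction it belongs to is not.

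Neither output gives the incidence of late ADRs.

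**4. Where are late reactions recorded?**

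| Late reaction (after day 30) | Protocol 6.3 | Protocol section 8.2 |
|---|---|---|
| Related to trabectedin | collected at the visit | to the sponsor's pharmacovigilance department; eCRF duty ended |
| PLD only, serious | collected at the visit | to the applicable marketing authorisation holder (8.2.1) |
| PLD only, non-serious | collected at the visit | no stated route |

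**5. Length of the gap.** Inputs: 21-day cycles (SAP 3.1), 30 days (SAP 5.4), a visit 12 months after Index (protocol 6.3). Assumptions: the Index date is the cycle 2 dose, the earliest allowed; there are no delays; 12 months is 365.25 days. With *c* total cycles:

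gap = 365.25 − [(c − 2) × 21 + 30] days.

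| Cycles | Window closes (days after Index) | Gap (days) | Gap (months) |
|---|---|---|---|
| 2 | 0 + 30 = 30 | 335 | 11.0 |
| 6 | 84 + 30 = 114 | 251 | 8.3 |
| 10 | 168 + 30 = 198 | 167 | 5.5 |
| 14 | 252 + 30 = 282 | 83 | 2.7 |
| 18 | 336 + 30 = 366 | none | none |

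With 6 cycles the gap is 251/365.25 = 69% of the year after Index. A patient treated for the full 12 months has only the visit a month after the Observation Period, so the gap is then small or absent.

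**The case against.** The strongest defence is that the SAP follows the protocol. Protocol 10.4.5 sets the same AE window, so this is not a SAP departure. The window is never attached to ADRs in so many words, and the table shells, which SAP 11 keeps in a separate document, might treat ADRs differently. This stands as a reason to call the ADR limit inferred and to amend both documents. It does not remove the problem, since the SAP 5.4 definition covers related events and all 17 titles agree.

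Several stronger readings are tempting, and the documents do not support them.
- *Late reactions appear nowhere in the SAP outputs.* Late deaths are summarised with cause, and late laboratory abnormalities may be. The accurate claim is that no AE or ADR table covers them.
- *A late reaction to PLD alone goes unreported.* Protocol 8.2.1 sends serious reactions to other drugs to the applicable marketing authorisation holder, with no 30-day limit. Only the non-serious ones lack a route under section 8.2.
- *The data are all in hand.* Under 8.2.2 some late events may never reach the eCRF. Recruitment closed on 31 July 2018, before this protocol version of 18 September 2018, so follow-up visits may already have passed under the unclear rule.

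There is also a fair warning about the remedy. SAP 9.5.1 counts ADRs of unknown relationship as related to both drugs. Follow-up may be by telephone, and patients may be on other therapy by then. Applying that rule to late events could attribute them to trabectedin and PLD without a judgement. The fix has to handle this.

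**Conclusion.** The concern holds in a limited form. As written, a reaction judged related to trabectedin or PLD that starts more than 30 days after the last dose enters none of the planned AE or ADR tables, although protocol 6.3 collects it. The ADR and SADR incidences would be understated to that extent. Separately, protocol 6.3 and 8.2.2 contradict each other on what is recorded after day 30 and need to be reconciled.

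The interval concerned depends on cycles received, under the assumptions stated for the calculation. It measures calendar time, not assessments: normally one visit or call falls in it, and only for patients who stopped trabectedin early, are alive and have not withdrawn consent. The documents give no rate of late reactions, so the number of patients affected is unknown; multiplying an assumed rate by 300 would only restate the assumption. This is a worthwhile, inexpensive improvement to safety reporting and does not touch the primary endpoint.

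**What to change.** Keep the 30-day window for all-causality AEs and leave the existing treatment-emergent tables unchanged.

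- **SAP 5.4, 9.5.1 and 11.1, and protocol 10.4.5:** state the ADR window explicitly. Add a separate table or listing of ADRs and SADRs related to trabectedin, PLD or both, with onset more than 30 days after the last dose. Show events of unknown relationship on their own line there, not counted as related to both drugs.
- **Protocol 6.3 and 8.2.2:** reconcile them so that one rule says where late ADRs to either study drug are recorded, including non-serious reactions to PLD alone.
- **Footnote to the new output:** ascertainment after day 30 is incomplete, because it rests on one visit or call in patients who stopped early and because sites following 8.2.2 may not have entered late events in the eCRF.
- **SAP 10:** mention the added output, so that the statement on changes from the protocol stays accurate until 10.4.5 is amended.

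The cost is one or two outputs, a few sentences in the SAP and a protocol clarification. The downsides are that late events will be unevenly captured across patients and that the reported reactions may look slightly less favourable. No visit, treatment or effectiveness analysis changes.
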